Title page

Effect of underdilated-stent technique on post-transjugular intrahepatic
portosystemic shunt encephalopathy

NCT Number: NCT ID not yet assigned

Document date: 2024-09-29

Study Protocol

1. Research Methods

(1) Eligibility Criteria

Inclusion Criteria:

- Liver cirrhosis, defined by clinical manifestations, biochemical indicators, imaging examinations, or liver biopsy;
- History of esophagogastric variceal bleeding, or refractory/recurrent ascites;
- Intended to undergo TIPS treatment.

Exclusion Criteria:

- Non-cirrhotic portal hypertension;
- Previous treatments that may affect portal pressure, such as TIPS or surgical procedures;
- History of overt hepatic encephalopathy (West-Haven classification ≥ 2);
- Malignant tumors in advanced stages;
- Concomitant irreversible heart, liver, kidney, or respiratory failure;
- Unable or unwilling to sign the informed consent form.

Withdrawal Mechanism

- Patients or their relatives may request study discontinuation during the trial.

(2) Randomization and Intervention

This study employed computer-generated randomization using sequentially numbered envelopes containing treatment protocols. Enrolled participants signed written informed consent forms and were randomly assigned to Group A or B. Participants remained unaware of their assigned group throughout the study. Both groups of patients received identical management protocols throughout the perioperative process, including preoperative consultation, preparation, monitoring, medication administration, surgical procedures, material handling, and postoperative follow-up. The sole difference was the use of 8mm (Group A) and 6mm (Group B) balloons for dilation of puncture tract and subsequently placed portosystemic stent during TIPS procedures. Neither group was administered drugs which might result in pathophysiologic affection of hepatic encephalopathy (e.g., lactulose, rifaximin, ornithine aspartate, branched-chain amino acids, or arginine) before or after TIPS.

(3) Sample Size Calculation

According to literature, the estimated 12-month incidence of overt hepatic encephalopathy following 8mm balloon full-dilation and 6mm balloon sub-dilation in TIPS patients was 54% and 20%, respectively. With a significance level of 5%, power of 80%, and a projected dropout rate of 10%, this study required 36 patients per group (two-tailed test).

(4) Follow-up and Outcomes

All enrolled patients underwent scheduled follow-up examinations at 1, 3, 6, and 12 months after TIPS procedure. The primary outcome was the incidence

of overt hepatic encephalopathy (West-Haven classification ≥ 2), while secondary outcomes included improvement of portal hypertension complications (e.g., esophageal variceal bleeding, worsening ascites), liver function, complications, and transplant-free survival.

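### Does the protocol go wrong by not stratifying randomisation, or the bleeding and ascites outcomes, by TIPS indication?

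*Protocol*

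**What the plan says.** Under Eligibility Criteria, either of two histories qualifies a patient: "History of esophagogastric variceal bleeding, or refractory/recurrent ascites". The two are joined by a plain alternative, so a patient may have both. No cap or planned mix is set.

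Under Randomization and Intervention, the method is given in one sentence: "This study employed computer-generated randomization using sequentially numbered envelopes containing treatment protocols". Participants "were randomly assigned to Group A or B". The text mentions neither blocks nor strata, and it does not say that there are none.

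Under Sample Size Calculation, the size rests on overt hepatic encephalopathy alone. The assumed 12-month incidence with the 8 mm and 6 mm balloon "in TIPS patients was 54% and 20%, respectively", which leads to 36 per group.

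Under Follow-up and Outcomes, the primary outcome is the incidence "of overt hepatic encephalopathy (West-Haven classification ≥ 2"), which applies to every patient whatever the indication. One secondary item is "improvement of portal hypertension complications (e.g., esophageal variceal bleeding, worsening ascites"). No population is stated for either event.

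**The concern.** Bleeding and ascites are different reasons for TIPS, and the complication the shunt is meant to control differs between them. If the indication also predicts encephalopathy, a trial of 72 patients with about 36 × 0.54 + 36 × 0.20 = 26.6 expected events looks small enough for an unlucky split to matter.

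The secondary outcomes raise a second worry. A smaller shunt might give up some control of bleeding or ascites, and that is the natural check on the 6 mm arm. If patients who could not have the event are counted in the denominator, the absolute difference shrinks. For example, suppose half the patients have ascites, control is 80% against 60% among them, and everyone else counts as uncontrolled. The pooled figures are then 40% against 30%, and a 20-point loss reads as 10.

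The suggested remedy would be one envelope series per indication, a stratified primary test and secondary outcomes reported by indication.

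**Working it through.** **The protocol's own figure.** Inputs from Sample Size Calculation: 54% and 20%, two-sided 5%, power 80%, dropout 10%. With mean rate 0.37 and pooled variance under the null:

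n = [1.96·√(2·0.37·0.63) + 0.8416·√(0.54·0.46 + 0.20·0.80)]² / 0.34² = (1.338 + 0.538)² / 0.1156 = 30.4, so 31 per group.

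31 / 0.90 = 34.4, so 35, against 36 stated. The figure reproduces to within one patient. Stratification does not enter it and would not change it.

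**How often the arms would differ in indication.** The protocol gives no mix, so the ascites share is assumed. With K ascites patients among 72 and 36 per arm, the number k in one arm is hypergeometric and the arms differ by |2k − K|/36.

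| K (share) | P(≥15 points) | P(≥20 points) |
|---|---|---|
| 7 (10%) | 1.1% | 0.0% |
| 14 (20%) | 13.5% | 3.5% |
| 24 (33%) | 21.1% | 7.9% |
| 29 (40%) | 14.9% | 5.4% |
| 30 (42%) | 23.2% | 9.4% |
| 36 (50%) | 23.8% | 9.8% |

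The figures do not rise smoothly because an odd K allows only odd differences. The root-mean-square difference is 11 to 12 points for shares of 33% to 50%.

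**What that does to the primary estimate.** The shift is the imbalance times the gap in encephalopathy risk between indications. The protocol gives no such gap. With a marginal rate of 37%, equal shares and assumed odds ratios of 2, 3 and 5, the gap is 16, 25 and 35 points. A 20-point imbalance then shifts the difference by 0.20 × 16 = 3.2, 0.20 × 25 = 5.0 or 0.20 × 35 = 7.0 points. A typical imbalance of 12 points at odds ratio 3 gives 0.12 × 25 = 3.0.

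For scale, the standard error of the difference at 36 per arm is √[(0.54·0.46 + 0.20·0.80)/36] = √(0.4084/36) = 0.107, or 10.7 points. A 5-point shift is 5.0/10.7 = 0.47 standard errors and 5/34 = 15% of the planned difference.

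**What stratifying would gain.** Power at 32 evaluable patients per arm (about 36 × 0.90), with equal shares. The plain chi-square test has 83.1% by exact enumeration. The other figures are simulated.

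| Assumed odds ratio | Stratified allocation and Cochran–Mantel–Haenszel test | Same test on an unstratified list |
|---|---|---|
| 2 | about 83.5% | about 82.8% |
| 3 | about 84.5% | about 84% |
| 5 | about 87% | about 86.5% |

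The full gain is under half a point at odds ratio 2 and about 1.4 points at 3. The stratified test on an unstratified list falls slightly below the plain test at odds ratio 2, and to about 82% if indication does not matter at all.

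**The secondary item.** The events named are variceal bleeding and worsening ascites. Rebleeding and control of existing ascites are not named. A patient enrolled for ascites can bleed for the first time, and one enrolled for bleeding can develop ascites. All patients are therefore plausibly at risk of both, and the fall from 80% against 60% to 40% against 30% belongs to an outcome the protocol does not state.

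Suppose nevertheless that an event occurs only in the relevant half, at 10% against 30% (assumed). The pooled rates are 0.5 × 10% = 5% and 0.5 × 30% = 15%. Power is 29% with 36 per arm, against 32% in the relevant 18 per arm. The absolute difference halves, the ratio is unchanged, and power is low either way because the sample is small.

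**The case for a change.** The strongest reply is that an analysis plan cannot create stratified allocation afterwards. It has to exist before the first envelope is opened, so the protocol is the place to name it. That is right, and stating whether the list is stratified would be good practice. It does not make an unstratified list invalid. Simple randomisation supports the planned comparison, and the gain forgone is small unless indication is a strong predictor.

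It can also be said that a reader weighing less encephalopathy against lost efficacy wants event rates among the patients concerned, and that the wording of the secondary item is loose: improvement and worsening sit in the same phrase, and improvement of ascites has no clear meaning in a patient without it. The looseness is real, and reporting by indication would help the reader. But which patients contribute to each secondary outcome, and whether the primary test is adjusted, are commonly fixed in the analysis plan. The protocol does not say that the analysis will be pooled over everyone.

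The remedy has a gap of its own. Because the entry criterion allows both histories, separate envelope series for bleeding and ascites would need a rule for patients who have both.

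**Conclusion.** The concern does not hold. That the allocation is unstratified and the secondary outcomes pooled is inferred from silence. Even if both are so, the primary test remains valid, because chance imbalance is part of what the 5% type I error covers. The cost is some precision: about 1.4 points of power at an assumed odds ratio of 3, under half a point at 2 and about 4 points at 5. A 20-point imbalance, itself a 5% to 10% event at ascites shares of 33% to 50%, shifts the primary estimate by 3 to 7 points over those odds ratios, against a planned 34.

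All these sizes rest on an indication mix and a risk gap that the document does not give. Only a very strong link between indication and encephalopathy would make stratification matter much for the primary outcome, and the protocol states none. The dilution argument replaces the named events with others. What is left is useful detail that could be stated, and a preference about design. No figure or rule in the protocol is shown to be wrong.

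### The bar on encephalopathy drugs before or after TIPS is not limited to prophylaxis and makes no exception for treating an overt episode

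*Protocol*

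**What the plan says.** Protocol, section 1(2) Randomization and Intervention: "Neither group was administered drugs which might result in pathophysiologic affection of hepatic encephalopathy". The sentence then gives examples and a time span, with the full object reading "pathophysiologic affection of hepatic encephalopathy (e.g., lactulose, rifaximin, ornithine aspartate, branched-chain amino acids, or arginine) before or after TIPS". The bar is defined by what a drug acts on, and the named drugs are only examples.

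Two sentences before it, the same section promises identical management in both groups. The items listed there include "monitoring, medication administration, surgical procedures, material handling, and postoperative follow-up", all placed under the perioperative process.

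Section 1(1) excludes patients with a "History of overt hepatic encephalopathy (West-Haven classification ≥ 2") and gives one route out of the study, a request by the patient or relatives. Section 1(4) makes the primary outcome the incidence "of overt hepatic encephalopathy (West-Haven classification ≥ 2), while secondary outcomes included improvement of portal hypertension complications", with visits at 1, 3, 6 and 12 months. Section 1(3) plans on an "estimated 12-month incidence of overt hepatic encephalopathy following 8mm balloon full-dilation and 6mm balloon sub-dilation in TIPS patients was 54% and 20%, respectively".

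The protocol does not mention prophylaxis, rescue treatment or how an overt episode is to be managed.

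**The concern.** The trial counts overt encephalopathy as its main event and expects it in more than a third of patients. The same protocol bars drugs that act on encephalopathy, with no stated end. A clinician who follows the sentence as written could not give such a drug to a patient who has just reached grade 2. A clinician who gives it departs from the written rule, and nothing says from what point this is acceptable.

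Two things are at stake. The first is safety: the literal rule withholds drug treatment from the patients who have the condition being studied. The second is conduct: each treated episode becomes a deviation, and the start of treatment is left to individual judgement.

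**Working it through.** **Inputs.** From Protocol section 1(3): 12-month rates of 54% (Group A, 8 mm) and 20% (Group B, 6 mm), 5% two-sided significance, 80% power, 10% dropout, 36 per group. The bar is in section 1(2) and the outcome definition in section 1(4).

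**The plan's own sample size.** Two proportions, pooled variance under the null, no continuity correction. The mean rate is (0.54 + 0.20)/2 = 0.37.

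- n = [1.960 × √(2 × 0.37 × 0.63) + 0.842 × √(0.54 × 0.46 + 0.20 × 0.80)]² / (0.54 − 0.20)²
- n = [1.338 + 0.538]² / 0.1156 = 30.4, rounded up to 31
- With dropout: 31/0.9 = 34.4, rounded up to 35

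This is one patient short of the stated 36, so the planning figures are coherent and can be used below.

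**Patients whom the literal bar would still cover after an episode** (expected number = patients × rate).

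| | Group A | Group B | Both | Share | A minus B |
|---|---|---|---|---|---|
| All 36 per group followed | 36 × 0.54 = 19.44 | 36 × 0.20 = 7.20 | 26.64 of 72 | 37% | 12.24 |
| 10% dropout, dropouts add no events (36 × 0.9 = 32.4 per group) | 32.4 × 0.54 = 17.50 | 32.4 × 0.20 = 6.48 | 23.98 of 64.8 | 37% | 11.02 |

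**Does the text limit the bar?** Four places could do so.

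1. *The sentence itself.* It covers the time after TIPS without an end and does not refer to prophylaxis.
2. *The identical-management sentence.* It is framed as perioperative, which points to a narrow meaning. But its list runs on to postoperative follow-up, and section 1(4) takes follow-up to 12 months. It does not confine the bar to the procedure.
3. *The exclusion of prior overt encephalopathy.* This implies that drugs given before TIPS would normally be preventive. It says nothing about a patient whose first episode comes after TIPS.
4. *The withdrawal route.* Only the patient or relatives can start it, so no investigator-led exit takes a patient with an episode out of the rule.

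Together these make a prophylaxis-only intention likely. None of them states it.

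**The case against.** The best defence is that the sentence has an obvious purpose: to keep co-medication from masking the effect of balloon size. With the perioperative framing and the exclusion of prior overt encephalopathy, the natural meaning is no prophylaxis, and nobody intends to leave an overt episode untreated. That defence largely stands. It makes this an ambiguity with a possible safety consequence, not a demonstrated ban on treatment. It does not remove the need to say so, because a bar on drugs for the very condition being counted should not depend on inference. Nor is it a matter for the statistical analysis plan. That document can say how treated episodes are analysed, but permission to treat belongs in the protocol.

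A reader might infer more than the text supports:

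- *That about 27 patients will be denied treatment.* The figure is the expected number of primary events. How many would go untreated depends on how the sentence is applied, which the protocol does not show.
- *That the bar biases the primary comparison.* It applies equally to both arms, so by itself it does not bias a comparison of first episodes.
- *That the trial loses power because drugs started on suspicion hide events.* Section 1(2) says only "Participants remained unaware of their assigned group throughout the study", so treatment that differs by arm is conceivable. Under the literal rule, though, such treatment would be a breach, and the effect on power has no fixed sign. By the same pooled approximation at 36 per group, power is 86% with no uncounted episode. One uncounted episode gives 80% if it falls in A, 92% if it falls in B, and 88% with one in each arm. Nothing in the protocol points to one of these cases.
- *That sites will read the rule differently.* The protocol does not mention more than one site.

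**Conclusion.** The concern holds as a gap in a stated rule. The bar on drugs acting on encephalopathy is not restricted to prophylaxis, has no end and has no exception for an overt episode. The group it touches is large, at 37% of patients on the planning rates with or without dropout, and more of them are expected in Group A.

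The size rests on the section 1(3) rates being right, on counting each patient once at a first episode, and, for the lower figure, on dropouts contributing no events. The consequence is for safety and for adherence to the written rule. The sample size and the first-episode comparison are not called into question.

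**What to change.** Replace the sentence in section 1(2) with wording such as: *Neither group receives these drugs as prophylaxis before or after TIPS. The restriction ends once a first overt episode (West-Haven grade 2 or higher) has been graded and documented, after which standard treatment is allowed in both groups by the same rule.* Record the date on which the episode was graded and the start date of any such drug.

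As long as the grade is documented before treatment starts, a first-episode primary outcome is unchanged. If prophylaxis was always meant, the new text only says so.

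The cost is one reworded sentence and two date fields on the case report form, with no extra patients. There is one downside. Treatment after an episode will be more frequent in Group A if the planning rates hold, so liver function and transplant-free survival should be read as effects of the whole strategy, including treatment of the encephalopathy it brings.

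### Does sizing the trial on a 12-month proportion with 10% dropout mean that early deaths and transplants are miscounted in the primary outcome?

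*Protocol*

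**What the plan says.** Under Sample Size Calculation (section 1(3)), the protocol takes from the literature "the estimated 12-month incidence of overt hepatic encephalopathy following 8mm balloon full-dilation and 6mm balloon sub-dilation", which "in TIPS patients was 54% and 20%, respectively". The other inputs and the result are "With a significance level of 5%, power of 80"%, and "a projected dropout rate of 10%, this study required 36 patients per group (two-tailed test").

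Under Follow-up and Outcomes (section 1(4)), visits are at 1, 3, 6 and 12 months. "The primary outcome was the incidence" of overt encephalopathy, West-Haven grade 2 or higher. The secondary outcomes cover bleeding, ascites, "liver function, complications, and transplant-free survival".

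The Withdrawal Mechanism (section 1(1)) is one sentence: "Patients or their relatives may request study discontinuation during the trial".

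No section names a test, an estimator, an analysis set, or a rule for patients who die or are transplanted before encephalopathy.

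**The concern.** The patients have cirrhosis with variceal bleeding or refractory or recurrent ascites, and transplant-free survival is an outcome, so some deaths and transplants within the year are to be expected. The sizing, however, knows only three states: encephalopathy by 12 months, none by 12 months, and dropout. A patient who dies without encephalopathy at month 2 fits none of them cleanly. Counted as free of encephalopathy, the death improves that group's result. Counted as a dropout, the patient is removed because of something that happened after randomisation.

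The arms might also differ in mortality. The randomised difference is the degree of dilation, and the secondary outcomes include complications of portal hypertension. If the 6 mm group had more early deaths, counting deaths as event-free could make underdilation look better against encephalopathy than it is. Withdrawal at the relatives' request adds a further worry, because a confused patient's relatives may act around the time of the primary event. At stake would be the direction of a small treatment difference and a few points of power.

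**Working it through.** **Inputs.** From section 1(3): 54% and 20%, two-sided 5%, power 80%, dropout 10%, 36 per group. Equal allocation follows from the equal group sizes. The document gives no death or transplant rate, so every such rate below is an assumption, with a constant hazard.

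**1. The plan's own figure.** The mean of the two rates is 0.37 and their difference is 0.34. With one common variance,

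n = 2 × 0.37 × 0.63 × (1.960 + 0.842)² / 0.34² = 0.4662 × 7.849 / 0.1156 = 31.65, so 32 per group.

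With dropout, 32/0.9 = 35.6, so 36, as stated. The variant with separate variances under the alternative gives 30.4, so 31, and 31/0.9 = 34.4, so 35, which is one patient fewer. Exact power of the uncorrected chi-square test at 32 per group is 83.1%.

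**2. Deaths and transplants counted as event-free.** Let λ = −ln(1 − p) be the encephalopathy hazard and δ = −ln(1 − q) the hazard of death or transplant, where p and q are the 12-month net risks. The observed encephalopathy rate is λ/(λ + δ) × [1 − exp(−λ − δ)]. With 32 per group:

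| Assumed q, both arms | Observed rates | Exact power |
|---|---|---|
| 10% | 51.6% v 19.0% | 80.4% |
| 15% | 50.4% v 18.5% | 78.9% |
| 20% | 49.1% v 18.0% | 77.4% |
| 25% | 47.8% v 17.5% | 75.8% |

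**3. The same patients excluded.** Only those who die or are transplanted before encephalopathy leave. This gives 30 and 29 patients with power 81.3% at q = 10%, 80.0% at 15%, 77.0% at 20%, and 26 and 25 patients with 75.2% at 25%. A harsher version removes a fraction q of everyone and keeps the rates at 54% and 20%. By the normal approximation, power at q = 10% is then 78.2%, with 36 × 0.9 × 0.9 = 29.2 patients per group, against about 82% with no such loss.

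Both calculations take 54% and 20% as rates free of competing deaths. If the literature figures are already net of deaths, or the 10% already includes them, nothing changes and 36 stands.

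**4. Can the comparison be tilted?** Suppose encephalopathy has the same hazard in both arms (net risk 37%), with assumed death risks of 10% in group A (8 mm) and 30% in group B (6 mm). Here λ = 0.462 and δ = 0.105 and 0.357. The observed rates are 35.3% v 31.5%. The difference of 3.7 points is about 0.037 × 32 = 1.2 patients. The exact chance of a false result favouring B rises from 2.7% to 5.1%.

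- Swapping the two death risks reverses the rates to 31.5% v 35.3%. With the planned effect, 30% in A and 10% in B gives 46.5% v 19.0%, a difference of 27 points and power of about 67%.
- Excluding the deaths in the unswapped case gives 38% v 42%, again the opposite sign.

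So the direction depends on which arm has more deaths and on the counting rule. The protocol states neither.

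**5. Would a competing-risk analysis remove the effect?** With complete follow-up, the 12-month cumulative incidence with death and transplant as competing events is the number with encephalopathy divided by all randomised patients. The 35.3% and 31.5% above are exactly those quantities, and Gray's test compares them. Moving to that analysis would leave the difference where it is. The cause-specific hazard or a composite with death and transplant would treat it differently, and nothing in the protocol rules out either.

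**The case for a change.** The best case for the concern is that the definition of the primary outcome and the assumptions behind the sample size belong in a protocol, whatever the SAP adds. A 12-month incidence has no value for a patient who dies free of encephalopathy at month 2, and the protocol itself expects such patients. The scenarios also show that the sign of a small difference can hang on the counting rule, which is a good reason to fix the rule before data are seen.

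Part of this stands. The protocol does not say whether the 10% includes deaths and transplants, and a sentence on it would be useful. But silence is not a wrong choice. Sizing on two proportions does not bind the analysis to two proportions. Censoring, a composite and a competing-risk analysis all remain open, so an early death is not confined to being a success or an exclusion.

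The withdrawal argument adds little. The sentence grants a right to stop. It does not say that data already collected are discarded or that later status may not be sought. If relatives act because of overt encephalopathy, the primary event may already have been recorded. Nor would excess deaths in one arm be hidden, because transplant-free survival, bleeding and ascites are all outcomes.

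**Conclusion.** The concern does not hold. The 36 per group reproduces, no stated figure is shown to be wrong, and the miscounting of deaths is inferred rather than written. What is absent, the rule for death or transplant before encephalopathy, is detail that commonly sits in the SAP, which is not shown.

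In size, power stays at or above 80% when 10% of patients are assumed to have a competing event, whether they count as event-free or those who had it before encephalopathy are excluded. It falls to about 75–76% only at an assumed 25%. The harsher removal in addition to the 10% dropout gives 78% at an assumed 10%. All of this rests on constant hazards, on mortality the document does not supply, and on reading 54% and 20% as free of competing deaths. The possible tilt in the comparison is about one patient per group under an assumed 10% v 30% split of deaths, and it changes sign when the split is reversed.

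### Do fixed visits at 1, 3, 6 and 12 months miss encephalopathy between visits and undercut the stated power?

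*Protocol*

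**What the plan says.** Protocol section 1.(4), Follow-up and Outcomes, makes two separate statements.

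- On the schedule: "All enrolled patients underwent scheduled follow-up examinations at 1, 3, 6, and 12 months after TIPS procedure".
- On the endpoint: "The primary outcome was the incidence" of overt hepatic encephalopathy, at West-Haven grade 2 or above. The same sentence lists the secondary outcomes, which include variceal bleeding, worsening ascites, complications and transplant-free survival.

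Section 1.(3), Sample Size Calculation, plans on "the estimated 12-month incidence of overt hepatic encephalopathy", which after full dilation and sub-dilation "in TIPS patients was 54% and 20%, respectively". The other inputs are 5% two-sided significance, 80% power and 10% dropout, and the result is "36 patients per group".

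No sentence says that grading takes place only at the visits. None says how an episode between visits is documented or graded.

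**The concern.** The four examinations are the only observation points the protocol names, and the last gap, from month 6 to month 12, is six months long. A West-Haven grade describes a patient's state when examined. If overt encephalopathy can start and resolve within a gap, a grade taken only on visit days records something nearer to point prevalence than to a 12-month incidence.

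Missed episodes would lower both event rates and shrink their difference. The trial has little spare power, so even modest under-capture would take it below 80%. Episodes never written down could not be recovered by any later analysis. The outcome sentence gives no time window either, so on a strict reading two assessors could count different events.

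**Working it through.** **Inputs from section 1.(3).** p1 = 0.54, p2 = 0.20, two-sided alpha 0.05, power 0.80, dropout 10%, 36 per group.

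**Step 1: reproduce the sample size.** Two proportions, pooled variance under the null, no continuity correction, mean rate p = (0.54 + 0.20)/2 = 0.37:

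n = [1.960 × √(2 × 0.37 × 0.63) + 0.842 × √(0.54 × 0.46 + 0.20 × 0.80)]² / 0.34²

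= (1.338 + 0.538)² / 0.1156 = 30.4, so 31 evaluable per group.

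With dropout, 31 / 0.90 = 34.4, so 35 per group against 36 stated. The arcsine formula gives 34, the unpooled formula 32 and the continuity-corrected formula 42. The stated figure is in order.

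**Step 2: power if some affected patients are missed.** Let s be the share of affected patients who are detected, equal in both arms. The protocol gives no value for s, so the range is an assumption. Observed rates become 0.54s and 0.20s. Evaluable patients number 36 × 0.90 = 32.4, taken as 32 per group.

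| s | Observed rates | Normal approx., n = 32 | Exact chi-square, n = 32 | Normal approx., n = 36 |
|---|---|---|---|---|
| 1.0 | 54.0% v 20.0% | 82% | 83.1% | 86% |
| 0.9 | 48.6% v 18.0% | 75% | 76.2% | 80% |
| 0.8 | 43.2% v 16.0% | 67% | 68.7% | 72% |
| 0.7 | 37.8% v 14.0% | 59% | 60.6% | 64% |
| 0.5 | 27.0% v 10.0% | 42% | 42.6% | 46% |

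The direction of the concern is therefore right under its premise. If between-visit episodes count and are recorded, s = 1 and nothing is lost.

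**Step 3: the extreme reading.** Suppose only visit-day status counted, each affected patient had one episode, and the hazard was constant over the year. An episode of 7, 14 or 30 days would then overlap one of the four visits in about 8%, 16% or 34-35% of affected patients. The durations are assumptions, and repeat episodes would raise these shares.

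**Step 4: is the premise in the text?** Set the passages side by side.

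- *Quantity.* Section 1.(3) plans on an incidence and section 1.(4) names an incidence. An incidence counts new events over a period, so status on four days would not be a natural reading of it.
- *Window.* Section 1.(3) uses 12 months and follow-up in section 1.(4) ends at 12 months. The window can be recovered and the two sections agree.
- *Role of the visits.* Bleeding and transplant-free survival stand under the same schedule. They happen between visits and cannot sensibly be scored as a state on a visit day. The coherent reading is that visits are contact points at which events since the last contact are collected.
- *Planning rates.* They are attributed to the literature, with no account of how episodes were found there. If those studies used a similar schedule, the 54% and 20% already contain the same under-capture, and the table in step 2 would discount it twice.

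**The case for a change.** The best argument for a change is that ascertainment of the primary outcome belongs in the protocol, because an analysis plan cannot restore episodes that nobody recorded. The protocol mentions no interval history, caregiver report, admission record or unscheduled assessment. The margin is thin: with the dropout allowance used up, missing one affected patient in ten takes power to about 76%. Two sentences and an interval-history form would close the gap without added visits or patients, at the price of some retrospective grading.

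Part of this stands. The outcome sentence does omit the 12 months, the handling of between-visit episodes is unwritten, and the conditional arithmetic is correct. What does not stand is the step from silence to a rule. The protocol nowhere confines grading to visit days, so the loss of power is a consequence of a reading the text does not call for. The remedy would keep the same four visits and would correct no stated rule or number. It would write down what counting incidence over 12 months already implies.

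**Conclusion.** No change is needed. The sample size is reproduced (35 against 36), and the planning quantity, the outcome and the length of follow-up are consistent with one another. Power would drop to between about 76% and 43% at 32 evaluable per group only if 10% to 50% of affected patients went undetected and the literature rates came from fuller ascertainment. The document supports neither condition.

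The omissions are real but small: the window is not repeated in the outcome sentence, and the recording of between-visit episodes is not described. Investigators asked for the incidence of overt encephalopathy would ordinarily ask at each visit what had happened since the last one. This conclusion rests on that ordinary practice. It would not hold if other trial documents restricted grading to the visit day.
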